Why is this young population at such high risk for severe and permanent osteopenia and skeletal fragility? The onset of AN most frequently occurs during adolescence, a period of maximal bone accretion, with  $> 90\%$  of bone mass accrued by 18 years of age (11). Because adolescence is a critical time for attainment of peak skeletal mass, reduction of BMD during this crucial period may lead to long-term morbidity. Indeed, we found that in contrast to normal adolescents who demonstrate marked bone accretion during puberty, adolescents with AN do not increase their bone mass (12). Therefore, bone mass remains low in these girls during a critical period in normal bone development. We have previously shown that adults with onset of AN during adolescence have lower spine BMD than those with adult-onset AN, despite comparable years of amenorrhea (13). Furthermore, low bone mass in adolescents with AN may be permanent despite recovery (14). Approximately half of young women with AN have persistent osteopenia, even after  $>10$  years (15-17). Therefore, there may be a narrow “window-in-time” during adolescence in which maximal accrual of bone mass occurs and during which treatment paradigms to maximize bone accrual must be implemented.

The overall significance of this problem: A large number of adolescent girls suffer from anorexia nervosa resulting in major deficits in bone mass and increased skeletal fragility, which may be permanent. Our proposed study will 1) test the efficacy of replacing a deficiency of an

endogenous bone anabolic hormone, IGF-1, with estradiol as a unique therapy for the low bone formation state in adolescents with AN and 2) enable an understanding of the effects of this disease and its treatment by measuring not only compartment-specific changes in bone density, but microarchitecture and strength at weight bearing and non-weight bearing sites.

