## RESEARCH DESIGN AND METHODS

Briefly describe study design and anticipated enrollment, i.e., number of subjects to be enrolled by researchers study-wide and by Partners researchers. Provide a brief summary of the eligibility criteria (for example, age range, gender, medical condition). Include any local site restrictions, for example, "Enrollment at Partners will be limited to adults although the sponsor's protocol is open to both children and adults."

Over the proposed 5 year grant, 100 girls with AN and 36 healthy controls will be enrolled at MGH. We will screen up to 272 subjects. Subjects with AN will be randomly assigned by the MGH Research Pharmacy to one of two arms: (i) IGF-1 with estrogen or (ii) estrogen alone with placebo for 12 months. Healthy controls will be followed prospectively for 12 months. Control subjects will complete the screen and baseline visit only. Study staff will follow-up with control subjects via a telephone call at 12 months after their baseline visit. This telephone call will serve to inform study staff of any medical changes or major life events that have occurred since the baseline study visit. We anticipate a 20% dropout rate based on our previous studies. Only AN subjects will take calcium and vitamin D supplement pills daily; dosage of vitamin D will be based upon each subject's serum levels.

AN Subjects: Subjects with AN will be 14-22 years old- an age span before peak bone mass is achieved, with a bone age (BA) of  $\geq 14$  years and meet DSM V criteria for AN. Our inclusion criteria for AN refers to the diagnosis of (a) Anorexia Nervosa or (b) Atypical Anorexia Nervosa with significant weight loss per DSM V. We will use a BA of 14 years as the cut-off because all epiphyses are near fusion and 98% of adult height has been attained at this skeletal age (19).

Control Subjects: (i) Healthy adolescent girls 14-22 years with a BA of  $\geq 14$  years; (ii) BMI between the 10th-90th percentiles for age, (iii) regular menstrual periods every 28-35 days and/or  $>9$  menses within the last 12 months for subjects  $\geq 2$  years post-menarche. Control subjects will be studied during the early follicular phase of their cycles (days 1-10).

Inclusion Criteria: AN:

- Subjects with AN will be 14-22 years old
- Bone age (BA) of  $\geq 14$  years
- Meet DSM V criteria for AN or Atypical AN with significant weight loss
- Subjects at MGH will be evaluated by an MGH study psychiatrist or psychologist before enrollment.

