(v) The Massachusetts Eating Disorders Association, which runs support groups for women and teenagers with eating disorders throughout eastern Massachusetts;

(vi) Health services at local colleges and universities such as Harvard University, Massachusetts Institute of Technology, Boston University, Boston College, Brandeis University, Emerson College, and Wellesley College

(vii) Facebook Advertisements. We also plan to use Facebook advertising to reach potentially interested subjects living in the Boston area. Women ages 18-45 living in New England will see advertisements for this research study in the "News Feed" section of their Facebook and be directed to an IRB approved RedCap prescreen survey. These advertisements will in no way be

designed to target individuals who indicate they may be struggling with an eating disorder on Facebook. The ads are shown to individuals based on the demographic requirements but have no link to any specific personal, profile or browsing history information. Examples of these advertisements are attached to this study protocol in Insight. A general Facebook page has also been created for this study (a Facebook requirement) and includes only basic contact and study information. A copy of this page is also attached to this study protocol in Insight.

(viii) Hasbro Children's Hospital at Rhode Island Hospital. We work with [name] and her team of providers to recruit subjects from Hasbro. This recruitment site will also function as an offsite clinic for follow up visits to provide Hasbro patients the opportunity to participate in the study with greater convenience. Subjects who are interested in the study can complete the eligibility portion of the screening visit at Hasbro and come to MGH for the consent process and baseline, 6 month, and 12 month visits. They will have the option to complete the entire 1, 3, 4.5, 7.5, 9, and 10.5 month visits at Hasbro.

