Effects of Anorexia Nervosa on Peak Bone Mass

NCT01301183

Version date: March 29, 2018

Analytical Plan

ANALYTIC PLAN

[name]., a Professor of Biostatistics at Harvard Medical School and co-investigator, has co-authored papers with us for more than 20 years and has been instrumental in our study design and will analyze these data. Data generated will be largely longitudinal. Measures of hormone function, bone turnover markers, nutrition, activity, body composition, bone density, bone microarchitecture and strength will be collected every three to six months for 12 months. There are three study groups: AN randomized to rhIGF-1 and transdermal estrogen, estrogen alone with placebo, and normal adolescents. Randomization will be performed by the MGH Research Pharmacy.

Analysis and interpretation are listed below for each aim and sub-aim:

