Sample Size Determination: The study is powered to our primary endpoints, (i) change in lumbar spine BMD (specific Aim 1A), and (ii) change in trabecular bone density (specific Aim 3A) in girls with AN who receive estrogen and rhIGF-1 versus estrogen alone. **Specific Aim 1A:** The primary analysis for this Specific Aim and the study is to compare the change in BMD over time in subjects with AN randomized to receive rhIGF-1 and estrogen (n=50) with the corresponding change in estrogen treated subjects (n=50). Using data from our previous study, we found that the variance covariance matrix of the random effects model was as follows: variance-intercept 0.01056, variance-slope 0.001523, covariance -0.001, and the residual variance around each subject's trajectory 0.000533. Based on these parameters, with 100 subjects with AN (50 in each group), we will have an 80% chance of detecting a significant (p=0.05 two sided) difference in change in lumbar spine BMD between girls who receive estradiol and rhIGF-1 versus estradiol alone if the true difference in slope between the groups is 0.03 g/cm²/year. This is a medically significant difference in that lumbar spine BMD in adolescents with AN is about 0.08 g/cm² lower than that in healthy adolescents at baseline. Estradiol alone has a net effect of 0.02 g/cm².year in increasing bone density, so an additional effect of 0.03 g/cm² (with rhIGF-1) added to 0.02 g/cm² (from estradiol alone) would be a net effect of 0.05 g/cm²/year (from estradiol and rhIGF-1). This would allow girls with AN to catch up to healthy adolescents. The sample size calculation, which assumes a 20% dropout rate, is based on the methods described by Yi and Panzarella (38) using the program <http://hedwig.mgh.harvard.edu/biostatistics/node/35>. The same model can be used with covariates and possible mediators of treatment effects such as baseline nutritional status, body composition, hormonal status, exercise and pubertal maturation. We will also explore the possibility that effects of rhIGF-1 with estradiol persist after discontinuation of treatment by examining bone density 12 months after stopping therapy.

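### Neither primary slope model includes an age term and no age stratum is named, although the protocol's own rationale makes age a likely driver of yearly bone accrual; the cost is a little precision, not bias

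*Protocol*

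**What the plan says.** **Eligibility.** Protocol, Research Design and Methods: "Subjects with AN will be 14-22 years old- an age span before peak bone mass is achieved". A bone age of at least 14 years is also required.

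**Rationale.** Protocol, Background and Significance, puts more than 90% "of bone mass accrued by 18 years of age" and suggests that "there may be a narrow “window-in-time” during adolescence in which maximal accrual of bone mass occurs".

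**Randomisation.** SAP, opening paragraph of the Analytic Plan: "Randomization will be performed by the MGH Research Pharmacy". The protocol says the same. Neither document names a stratification factor.

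**Primary model for lumbar spine BMD.** SAP, Sample Size Determination, Specific Aim 1A, compares slopes between arms in a random-effects model. On adjustment it says only "The same model can be used with covariates", followed by a list of examples. The list is optional and open-ended. It includes pubertal maturation but does not name age.

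**Primary model for trabecular density.** SAP, Specific Aim 2B, uses random patient and slope effects and takes the group-by-time interaction as the measure of interest. No age term is given.

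**Elsewhere.** Pubertal status is firmly adjusted for only in Specific Aim 2C, which is an IGF-1 association analysis. No treatment-by-age interaction appears in the SAP.

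**The concern.** Both primary outcomes are changes over a year. If accrual slows between 14 and 22, as the protocol's rationale implies, girls at the two ends of the range have different expected slopes whichever arm they are in. Five of the nine single years of age in the range are 18 or over, so the spread around that point is wide.

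Leaving age out of the model puts this variation into the between-girl slope variance, which widens the confidence interval for the arm difference. With no stratum and no age term, a chance difference in age between arms would also feed into the estimate with nothing to correct it. Pubertal maturation is at best a partial substitute: its use is optional, and the bone-age floor of 14 narrows its range.

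**Working it through.** **Inputs from the SAP (Specific Aim 1A).** Slope variance 0.001523, residual variance 0.000533, difference to detect 0.03 g/cm²/year, 50 per arm, two-sided 0.05, 80% power, 20% dropout. The protocol places the scans at 0, 6 and 12 months.

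**Step 1. Reproduce the SAP's power.**
- The squared deviations of the times 0, 0.5 and 1 year from their mean sum to 0.5.
- Sampling variance of one girl's slope = 0.001523 + 0.000533/0.5 = 0.002589, so SD = 0.0509.
- With 50 per arm: SE = 0.0509 × √(2/50) = 0.01018; 0.03/0.01018 = 2.95; power 83.8%.
- With 40 completers per arm: SE = 0.01138; ratio 2.64; power 75.1%.
- If all dropouts leave after month 6 and their partial data are kept in the mixed model, power is 79.5%.

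The stated 80% is therefore reproduced under that last pattern, and I use it as the starting point (1.96 + 0.84 = 2.80 standard errors).

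**Step 2. Slope variance that age could explain.** The documents give neither an age gradient nor an age mix. I assume ages spread uniformly over 14-22 and expected accrual changing linearly by a total of g across that range. The variance due to age is then g²/12. Adding age-by-time removes it, the arm-difference variance falls by the fraction (g²/12)/0.002589, and the 2.80 is divided by the square root of one minus that fraction.

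| g (g/cm²/year, assumed) | g²/12 | Share of slope variance 0.001523 | Fall in arm-difference variance | Power |
|---|---|---|---|---|
| 0.01 | 0.0000083 | 0.5% | 0.3% | 80.1% |
| 0.02 | 0.0000333 | 2.2% | 1.3% | 80.5% |
| 0.03 | 0.0000750 | 4.9% | 2.9% | 81.1% |
| 0.04 | 0.0001333 | 8.8% | 5.1% | 82.0% |
| 0.06 | 0.0003000 | 19.7% | 11.6% | 84.6% |

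For scale, the SAP puts the whole net effect of estradiol alone at 0.02 g/cm²/year.

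**Step 3. Chance imbalance.** Under the uniform assumption half the girls are under 18. The SD of the difference in that share between arms is √(0.25 × 2/50) = 0.10, so a gap of 20 points or more is two SDs, a chance of about 5%. The mean ages below and above 18 would be 16 and 20, half the 8-year range, so their expected slopes differ by g/2. A 20-point gap shifts the unadjusted arm difference by 0.20 × g/2 = 0.1g. That is 0.001 for g = 0.01 and 0.006 for g = 0.06, or 3% to 20% of the 0.03 target.

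**Step 4. What the trial can say about age.** Take the same half share and slope SD.
- Under-18s alone, 25 per arm: SE = 0.0509 × √(2/25) = 0.0144, power 55% for a difference of 0.03. With 20 per arm, power is 46%.
- A 0.03 difference in treatment effect between the two age groups: SE = 0.0509 × √(4/25) = 0.0204, power 31%. With 20 per arm in each group, power is 26%.

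**Trabecular density.** The SAP gives only an SD of 6% for relative change, with no variance components, so the gain there is not computed. The same reasoning applies.

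**The case against.** Several points on the other side stand.

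- **No bias.** Omitting age, as a stratum or a covariate, does not bias a randomised comparison.
- **The gradient is assumed.** The protocol's background reports that adolescents with AN do not increase their bone mass, which suggests that the normal age gradient may be blunted in this population. The table therefore starts at 0.01, where the gain is negligible.
- **Maturity is not ignored.** Pubertal maturation is on the SAP's optional list, and the list is open.

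A reader might also infer more than the documents support.

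- **That recruitment is confined to adults.** Item (vii) of the protocol's recruitment list does say "Women ages 18-45 living in New England will see advertisements for this research study", but this describes the Facebook route alone. Other routes include high-school health staff, pediatric practices, a child psychiatry service, support groups that include teenagers, and a children's hospital. The protocol describes referral mechanisms intended to maximise adolescent enrolment and provides for assent at ages 14-17. Changing the advertisement's age filter to 18-22 would reach no additional girl under 18.
- **That the age range contradicts the rationale.** More than 90% accrued by 18 leaves some accrual still to come, so it is compatible with 14-22 lying before peak bone mass. The adolescent window is itself stated only as a possibility.
- **That the trial's question is averaged away.** No stated aim asks whether the effect differs by age, and the protocol's section on selection of subjects names adolescents and young women aged 14-22 as the population. If the whole 0.03 effect fell in the under-18s and they were half the sample, the pooled effect would be 0.015 and power 26%-31%. That is a hypothetical about a subgroup, not a failure of the stated comparison.
- **That a separate peak-bone-mass conclusion should be drawn for under-18s.** At 46%-55% power, it would risk a false negative being read as a finding.

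**Conclusion.** The point holds as a modest improvement. No age stratum is named, and neither primary slope model has an age term, although the protocol's rationale makes age a likely driver of the outcome. For lumbar spine BMD the gain from adding it runs from almost nothing (80% to 80.1%) to about 5 points of power (84.6%), depending on an age gradient that the documents do not give. The figures also rest on a uniform age mix, a linear gradient, and the SAP's slope variance containing the age variation that the new term would remove. Protection against a chance age imbalance comes with the same term. The validity of the primary comparison is not in question.

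**What to change.** 1. In the SAP, pre-specify baseline age and age-by-time as covariates in both primary slope models, lumbar spine BMD and trabecular density, before treatment codes are opened.
2. Report the treatment-by-age interaction as exploratory, as an estimate with its confidence interval, and draw no separate conclusion for under-18s.
3. Stratify any remaining randomisation by age (under 18, 18 and over) where this is still feasible. If it is not, items 1 and 2 still stand.

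The cost is a few lines of SAP wording and, if item 3 is possible, one stratum in the pharmacy's list. Age is already known for every subject, so no visits, tests or subjects are added. The interaction estimate will be imprecise, and the report should say so.

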Inclusion Criteria: Controls:

- Healthy adolescent girls 14-22 years
- BA of  $\geq 14$  years
- BMI between the 10th-90th percentiles for age
- Regular menstrual periods every 28-35 days and/or  $>9$  menses within the last 12 months for subjects  $\geq 2$  years post-menarche.

Exclusion Criteria:

- Diseases known to affect bone metabolism including untreated thyroid disease, Cushing's syndrome, diabetes, pituitary disease, renal failure and prior bone fracture within six months of the study.
- Medications known to affect bone metabolism, including gonadal steroids and excluding oral contraceptives or estrogen/progestin containing compounds within two months.
- Evidence of suicidality, psychosis, or substance abuse based on an interview with the study psychiatrist or psychologist and recommendations.
  - In the event that evidence of suicidality, psychosis or substance abuse is uncovered in the interview, the current treatment team for the subject will be contacted and informed by the current study psychologist or psychiatrist. In the event a subject does not have a treatment team in place, referrals will be made by the current study psychologist or psychiatrist. If danger is imminent and safety can not be guaranteed, 911 can be called.
- Premature ovarian failure, as demonstrated by an elevated FSH.
- Abnormal TSH.
- Hematocrit  $<30\%$ , Potassium  $<3.0$  mmol/L, Glucose  $<50$  mg/dl
- Pregnancy
- History of malignancy
- Absolute contraindications to estrogen therapy (for girls with AN)

Briefly describe study procedures. Include any local site restrictions, for example, "Subjects enrolled at Partners will not participate in the pharmacokinetic portion of the study." Describe study endpoints.

Screening Visit: Eligibility for participation in the protocol will be determined at a screening visit. Evaluations on this visit will include:

- (a) History and physical exam including Tanner stage, height and weight.
- (b) Blood laboratory tests for glucose, TSH, LH, FSH, potassium and hematocrit, IGF-1, urine or serum pregnancy test and Bone age estimated using an x-ray of the left hand and wrist by standards of Greulich and Pyle (19).
  - i. In cases where the family can provide records of the lab work required for screening performed within two months of the screening visit, we will not repeat those labs.

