  - ii. Blood laboratory tests can be done at baseline visit if unable to obtain at screening visit. If blood laboratory tests are done at baseline, medications will be withheld until laboratory results are received and assessed.

Baseline Visit:

- (a) Bone age estimated using an x-ray of the left hand and wrist by standards of Greulich and Pyle (19) if not completed at the screening visit.
- (b) Complete History and Physical: Including growth, menstrual history, Tanner staging staging and fundoscopic exam.
- (c) Anthropometric Measurements: Height will be measured in triplicate using a stadiometer, and weight on a single electronic scale in the Clinical Research Center (CRC).
- (d) Nutritional Assessment: CRC dieticians at MGH will evaluate nutritional status using 4-day food records for macro- and micronutrient intake (Nutrition Data Systems, version 4, Minneapolis, MN) and indirect calorimetry (metabolic cart) to determine respiratory quotient (RQ) and resting energy expenditure. (All subjects consent to the metabolic cart, although it is treated as optional during the study. A food diary log may be provided at the screening visit or baseline visit. Although all subjects consent to the food diary log, its completion is treated as optional during the study.)
- (e) EDI2: Eating Disorders Inventory-2 questionnaire, which has been validated in adolescent patients with eating disorders (25) and includes assessment of body image. This is a 91-item, 11 scale, six-point forced-choice self-report inventory assessing behavioral and psychological traits common in AN. (This can be completed at the screen visit)
- (f) BDI-II: Beck Depression Inventory-2 questionnaire is a self-report inventory assessing depression and mood traits common in AN (All subjects consent to standardized psychiatric tests, although they are treated as optional during the study. This component can also be completed at the screen visit, instead of the baseline visit.). For safety concerns related to suicidality, after every administration of the BDI-II, a research assistant or study nurse will review the suicidality item of each measure. If any subject scores a “2” or “3” on the BDI-II “Suicidal Thoughts or Wishes” item, or if the total score corresponds to “moderate” or “severe” depression (see below), the study psychologist/psychiatrist will be paged for further assessment with the participant. BDI-II scoring ranges are as follows:
  - a. 0-13: minimal depression

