  - b. 14-19: mild depression
  - c. 20-28: moderate depression
  - d. 29-63: severe depression
- (g) STAI: State Trait Anxiety Inventory questionnaire is a 40-item and four-point Likert scale self-report inventory assessing state and trait anxieties common in AN. (All subjects consent to standardized psychiatric tests, although they are treated as optional during the study. This component can also be completed at the screen visit, instead of the baseline visit.)

- (h) Activity Assessment: Habitual exercise and activity will be assessed using a standardized exercise questionnaire, which provides a good estimate of past year physical activity in adolescents (26, 27). (All subjects consent to the activity assessment, although it is treated as optional during the study.)
- (i) Bone Turnover Markers: Serum for PINP and C-telopeptide (CTX).
- (j) Calcium Metabolism: Blood for calcium, phosphorus, 25(OH) D, 1,25(OH)2D, PTH.
- (k) Hormonal Evaluation: Serum for IGF-1, IGFBP-3, SHBG, estradiol, leptin.
- (l) If not obtained at screening visit: Blood laboratory work for glucose, TSH, LH, FSH, potassium and hematocrit, and IGF-1. Medications will be withheld until laboratory results are received and assessed.
- (m) Bone Mass Density: lumbar spine (AP and lateral), hip, radius, whole body areal BMD, BMC and BA will be measured by dual energy x-ray absorptiometry (DXA: Hologic QDR 4500, Waltham, MA).
- (n) Body Composition: Whole body DXA will be performed to assess fat and lean mass.
- (o) Bone morphology, microarchitecture and strength will be determined at the ultradistal radius and distal tibia using HR-pQCT (Xtreme CT, Scanco Medical AG). Bone strength will be determined using FEA of HR-pQCT scan data (28).
- (p) Safety Evaluation: Urine or Serum HCG (to rule out pregnancy) and fasting glucose.
- (q) Thigh and abdomen MRI and an L4 MR spectroscopy will be performed to assess bone marrow fat. We will also add Pref-1 assessment to the already collected blood. This will only be repeated at 12 months for patients with anorexia nervosa.
  - a. This study is optional for AN subjects and non-optional for HC subjects

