- (j) Activity Assessment: Habitual exercise and activity will be assessed using a standardized exercise questionnaire, which provides a good estimate of past year physical activity in adolescents (26, 27). (All subjects consent to the activity assessment, although it is treated as optional during the study.)

(k) Two subtests, Vocabulary and Matrix Reasoning, from the Weschler Abbreviated Scale of Intelligence (WASI), a Color-Word Interference Test subtest from the Delis Kaplan Executive Functioning Scale (DKEFS), and the California Verbal Learning Test (CVLT). (All subjects consent to the cognitive assessments, with the intention that they will be completed to the extent that time, subject schedule, and circumstances allow during the visit)

6-month and 12-month (AN Subjects Only): will include all the baseline procedures but the bone age x-ray.

Eligible consented subjects will be allowed to have CT scans performed between the screening and baseline visits if scheduling conflicts arise with the baseline visit. This will allow the subject to obtain a baseline assessment of bone microarchitecture prior to the initiation of rhIGF-1 supplementation. In the event that a CT cannot be performed on the scheduled baseline visit date due to unforeseen issues, willing subjects will be able to return within a 1 week window for this test. DXA scans can also be completed at screening visit if not able to be performed at baseline visit. MR/MRS will be repeated at 12 month visit for patients with anorexia nervosa. We will also repeat the Pref-1 levels for those who enrolled in this optional part of the study.

1-month, 4.5-month, 7.5-month and 10.5 month visits (AN Subjects Only): Evaluations on these visits will include:

- (a) History and physical exam, including height and weight
- (b) Pregnancy test
- (c) Serum IGF-1 and glucose

3-month and 9-month visits (AN Subjects Only): Evaluations on these visits will include:

- (a) History and physical exam, including height and weight
- (b) Pregnancy test
- (c) Serum IGF-1 and glucose
- (d) Nutrition evaluation will be assessed by using 4-day food records for macro- and micronutrient intake (Nutrition Data Systems, version 4, Minneapolis, MN)
- (e) Activity assessment: Habitual exercise and activity will be assessed using a standardized exercise questionnaire. (All subjects consent to the activity assessment, although it is treated as optional during the study.)
- (f) Bone turnover markers and hormones

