**Estrogen** administration in the doses being administered is associated with minimal possible side effects. Occasional side effects may occur, the most common of which are mild headaches, and very rarely some irritation or redness at the application site for transdermal estrogen. Adverse reactions that have been reported with estrogen therapy include abnormal bleeding patterns, changes in nature and quantity of vaginal discharge, tenderness and enlargement of breasts, nausea, vomiting, abdominal pain, bloating, gallbladder disease, rashes, intolerance to contact lenses, migraines, dizziness, depression, abnormal movements, and changes in weight. These adverse effects are, however, rare, and seen more commonly with the estrogen taken orally rather than transdermally. More serious side effects include hypertension, lipid and clotting disorders. These are more commonly seen in older women and in women with a family history of clotting disorders. Continuous estrogen administration without cyclic progesterone can predispose the uterus to cancer. Because we will be administering progesterone for ten days every month, this should not be a concern. We will monitor the subjects' blood pressure at each visit and will also determine through careful questioning and examination the appearance of any side-effect at each visit. Estrogen administration in pregnancy may be teratogenic. We will thus perform a pregnancy test prior to administering estrogen.

We will not enroll subjects with the following absolute contraindications to estrogen therapy:

- Known or suspected pregnancy
- Undiagnosed abnormal uterine bleeding
- History of clotting disorders such as thrombophlebitis and thromboembolic disorders
- Known or suspected cancer of the breasts, uterus or ovaries.

Relative contraindications such as migraines and smoking history will be decided on a case by case basis using history and physical findings

Subjects will be instructed to call us if they develop any side-effects of the medication. Subsequent management will be decided based on the severity of the side-effect.

Use of replacement or higher doses of estrogen before epiphyseal closure could accelerate growth plate closure resulting in an inability to reach the full potential for adult height. To avoid

this possible side effect, we plan to administer replacement estrogen doses transdermally to girls with a bone age of 14 or more years, who have achieved 98% of their adult height.

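### After entry, the only scheduled suicidality question is in the BDI-II, which is optional and has no stated substitute if declined (minor, safety only)

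*Protocol*

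**What the plan says.** **Entry.** The AN inclusion criteria state: "Subjects at MGH will be evaluated by an MGH study psychiatrist or psychologist before enrollment". The exclusion criteria include "Evidence of suicidality, psychosis, or substance abuse based on an interview with the study psychiatrist or psychologist and recommendations". If that interview uncovers a problem, the treatment team is informed, a referral is made where there is no team, and 911 is available for imminent danger.

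**After entry.** Baseline Visit item (f), repeated in the Combined Screening and Baseline Visit section, says of the BDI-II: "For safety concerns related to suicidality, after every administration of the BDI-II, a research assistant or study nurse will review the suicidality item". If the item scores 2 or 3, or the total is in the moderate or severe range, "the study psychologist/psychiatrist will be paged for further assessment with the participant". The same item also says: "All subjects consent to standardized psychiatric tests, although they are treated as optional during the study".

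**Repeats.** The 6- and 12-month visits, for AN subjects only, "will include all the baseline procedures but the bone age x-ray", so the BDI-II recurs there. The visits at 1, 3, 4.5, 7.5, 9 and 10.5 months list a history and physical but no psychiatric measure.

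**Item (p).** The baseline safety item reads in full: "Safety Evaluation: Urine or Serum HCG (to rule out pregnancy) and fasting glucose". It has no psychiatric content.

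**Other cover.** The estrogen risk text lists "migraines, dizziness, depression, abnormal movements, and changes in weight" among reported reactions and plans questioning about side effects at each visit. The second discontinuation criterion removes any subject found to meet an exclusion criterion. A physician can be paged at all times, and the DSMB, which includes a psychologist, reviews adverse events every six months.

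**The concern.** The protocol gives suicidality as the reason for reviewing the BDI-II item, yet the review happens only if an optional form is completed. The optional wording is the same as that used for the STAI, which has no stated safety role. A sentence that lets subjects skip a questionnaire therefore also lets them skip a safety check.

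As written, a treated subject aged 14 to 22 who declines the form each time can complete 12 months without a stated question about suicidal thoughts. The protocol treats suicidality as grounds for exclusion and, through the discontinuation criteria, for stopping. A criterion of that kind needs some planned way of finding the subjects to whom it applies.

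**Working it through.** The plan gives no figure on this point, so the check sets the texts side by side and counts.

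**1. Where suicidality is asked about on a schedule**

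| Time | Step | Can it be skipped as written? |
|---|---|---|
| Entry | Psychiatrist or psychologist interview | It is the basis of an eligibility criterion |
| Baseline | BDI-II item review | Yes, form optional |
| Month 6 (AN) | BDI-II item review | Yes, form optional |
| Month 12 (AN) | BDI-II item review | Yes, form optional |
| Months 1, 3, 4.5, 7.5, 9, 10.5 (AN) | None listed | – |

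Scheduled BDI-II reviews per AN subject: 1 + 2 = 3. Two fall after treatment starts, and only month 6 falls before the 12-month treatment ends. A subject who always declines has 0 of 3. The baseline review largely repeats the entry evaluation, so the loss is mainly at month 6, then month 12.

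**2. Does another provision fill the gap?**

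- *Second discontinuation criterion.* It imports the exclusion criterion and, with it, the interview, treatment-team contact, referral and 911. This is a response once suicidality is known. It schedules no question.
- *Side-effect questioning and history and physical.* These occur at each AN follow-up visit and could reach low mood, since depression is a listed reaction. Suicidality is not named, and suicidal thoughts arising from the illness need not be reported as a drug side effect.
- *Pager and call-in instructions.* They depend on the subject calling.
- *DSMB.* It reviews events already reported.

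All four give partial cover. None is a planned suicidality question for a subject who declines the form.

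**3. How many subjects**

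The documents give no decline rate. Per 10% of AN subjects declining at a follow-up visit:

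- no dropout yet: 0.10 × 100 = 10 subjects
- all of the planned 20% dropout has occurred: 0.10 × (100 × 0.80) = 8 subjects

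This is a scale for reading any decline rate, not an estimate of one.

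**4. What paging is lost**

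The item trigger is a score of 2 or 3. The total-score trigger covers moderate (20–28) and severe (29–63), that is, 20 or more. Both are lost for a subject who declines the form.

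**The case against.** The strongest reply is that the BDI-II text is a duty to act on answers collected for research, not a monitoring programme. It applies whenever the form is given, and the form sits among the questionnaires, not in the safety item. On that reading, optional and always reviewed when given do not conflict. The protocol is also a summary that does not itemise what a history and physical or side-effect questioning contains, so silence does not show that clinicians will not ask. The listed estrogen reactions, depression among them, are described as rare, and no suicidality risk is named for rhIGF-1.

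Much of this stands. There is no contradiction in the text, and good clinicians may well ask. What remains is that an explicit rule makes the one scheduled question skippable, and nothing states what replaces it.

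A reader might go further and infer that subjects who decline the form are unmonitored, or that the protocol has no route to the study psychiatrist or psychologist for them. The documents do not support that. The second discontinuation criterion, read with the exclusion criteria, supplies a specialist and emergency response, and clinical contact continues at every AN follow-up visit. Only scheduled detection is missing.

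**Conclusion.** The point holds as a minor safety gap: for AN subjects who decline the BDI-II, the available text schedules no suicidality question after the entry interview. The practical loss is one check during treatment (month 6) and one at its end (month 12).

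This rests on the visible text, from which some pages, including consent pages, were removed, and on reading the optional wording at face value. The number affected is unknown. The rule applies to both arms alike and has no bearing on the BMD or HR-pQCT endpoints, the sample size or the efficacy analyses.

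**What to change.** Add one line to Baseline Visit item (p): the BDI-II suicidal-thoughts item is completed or, if the form is declined, the same item is asked verbally by the clinician doing the history and physical. The existing wording for the 6- and 12-month visits then carries it forward.

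Use the same trigger (item score 2 or 3) and the same paging route for both modes, so that subjects who decline the form and those who complete it are handled alike. Record refusals, which the protocol's general right to skip any portion of a visit still allows. The rest of the BDI-II stays optional.

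**Cost.** No new instrument, staff or visit is needed. Assuming one minute each and everyone declining the form, the upper bound is 100 AN subjects × 3 visits + 36 controls × 1 visit = 336 minutes, and 336 / 60 = 5.6 hours. Limited to AN subjects it is 100 × 3 = 300 minutes, or 5 hours.

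**Downsides.** Some subjects will refuse the verbal item too, and the total-score trigger (20 or more) is still lost for anyone who declines the full form.
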